### 3 STUDY DESIGN

#### 3.1 Design

This is a randomized, open-label serologic study with enrollment of up to 180 adults aged 65-74 years in the first year (2016-17) and an additional 30 adults in the second year (2017-18) for a total of 210 across two years, at Marshfield Clinic Research Institute (MCRI). Subjects will be recruited from community-dwelling individuals who receive their inpatient and outpatient care from Marshfield Clinic facilities.

Randomization to one of three licensed influenza vaccine groups in the first year (2016-17) will be stratified by prior receipt of the 2015-16 influenza vaccine. The randomization algorithm will target enrollment of approximately 25% of subjects in the unvaccinated in 2015-16 stratum. It is anticipated that a percentage of the randomized study subjects may not complete the study.

Participants will be randomized to receive IIV3, HD-IIV3, or aIIV3 at their baseline study visit to ensure an appropriate minimum number of subjects receive high dose and adjuvanted vaccines in 2016-17 for analyses. Participants will be grouped according to vaccination type (standard dose, high dose or adjuvanted vaccine) received during the 2016-17 season (**Table 1**). All subjects enrolled in Fall 2016 will have a baseline serum blood draw, a second serum blood draw 28 ( $\pm 5$ ) days after vaccination and 6 months after vaccination in each season (2016-17 and 2017-18). In Fall 2017, participants who received HD-IIV3 and aIIV3 in Fall 2016 will receive the same vaccine type. Participants who received IIV3 will be randomized to receive HD-IIV3, aIIV3, or RIV4 for the 2017-18 season.

An additional 30 adults who received IIV3 in the 2016-2017 season will be recruited in Fall 2017. Newly recruited participants will be randomized to receive HD-IIV3, aIIV3, or RIV4 for the 2017-18 season and will have serum blood draw before vaccination, 28 ( $\pm 5$ ) days after vaccination and 6 months after vaccination.

Table 1. 2016-17 Vaccine Randomization & Blood Draw Scheme with Proposed ID numbering

	Group	2016-17 Vaccine	2017-18 Vaccine	Total
65-74 years	A	2016-17 HD-IIV3	2017-18 HD-IIV3	60
	B	2016-17 aIIV3	2017-18 aIIV3	60
	C1	2016-17 IIV3	2017-18 high dose trivalent inactivated influenza vaccine	30
	C2	2016-17 IIV3	2017-18 aIIV3	30
	C3	2016-17 IIV3	2017-18 RIV4	30
		Total		210

All participants will be contacted weekly throughout the influenza season to monitor for influenza-like illness and, if exhibiting symptoms, they will be scheduled for nasal and throat swabs to be tested for influenza.

Study follow-up will span approximately two years from the first dose for participants enrolled in the first year. Study follow-up will span approximately 6 months from their enrollment date for study subjects recruited in Fall 2017.

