### **2.2 Secondary Objectives**

- Compare immune responses as measured by virus neutralizing antibody titers, neuraminidase antibody mediated inhibition titers, and anti-human CD107a antibody titers among persons aged 65-74 years vaccinated with one of two licensed influenza vaccines: HD-IIV3 or allIV3 approximately 28 days, 6 months, and 12 months after receipt of the 2016-17 vaccine.
- Compare immune responses as measured by virus neutralizing antibody titers, neuraminidase antibody mediated inhibition titers, and anti-human CD107a antibody titers among subjects after repeat influenza vaccination (2016-17 and 2017-18) with HD-IIV3 and allIV3 with subjects vaccinated with IIV3 in 2016-17 and either HD-IIV3 and allIV3 in 2017-18 approximately 28 days and 6 months after receipt of the 2017-18 vaccine.
- Compare immune responses as measured by HI by prior receipt of 2015-16 influenza vaccine among persons aged 65-74 years vaccinated with one of two licensed influenza vaccines: HD-IIV3 or allIV3 approximately 28 days, 6 months, and 1 year after receipt of the 2016-17 vaccine.
- Compare immune responses as measured by HI among persons aged 65-74 years who received IIV3 in 2016-17 and vaccinated with one of three licensed influenza vaccines in

2017-18: HD-IIV3, aIIV3 or RIV4 approximately 28 days and 6 months after receipt of the 2017-18 vaccine.

- Compare immune responses as measured by HI among persons who received IIV3 in 2016-17 and vaccinated with one of two licensed influenza vaccines in 2017-18: HD-IIV3 or aIIV3 with subjects who received repeat influenza vaccination (2016-17 and 2017-18) with HD-IIV3 and aIIV3 approximately 28 days and 6 months after receipt of the 2017-18 vaccine.
- Conduct influenza surveillance to determine factors associated with vaccine failure (laboratory confirmed influenza) among study participants if it occurs during the surveillance period.

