## 3.3 Randomization Procedure

We will use stratified block randomization to ensure more even distribution of subjects with prior receipt of 2015-16 influenza vaccine. Subjects will be stratified based on receipt of 2015-

16 influenza vaccine. Within each group (vaccinated or unvaccinated in 2015-16), sequential enrollment numbers will be randomly assigned to each vaccine group in random blocks ranging from four to eight. This will ensure proper distribution of subjects across vaccine group assignment.

In Fall 2017, only participants who received IIV in 2016-17 will be randomized. We will use stratified block randomization and subjects will be stratified based on participation in this study during the 2016-17 season (previously participated or new recruit).

This is an open-label study, therefore the vaccine type will be known to the participant. Trained research staff will prepare and administer the influenza vaccine. Randomization to vaccination type will occur at the participant's first study visit after eligibility is confirmed and informed consent obtained. Those enrolled in year 1 who receive IIV3 will be randomized a second time at their fourth visit.

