## **5 SELECTION OF STUDY SUBJECTS**

### **5.1 Inclusion Criteria**

Subjects must meet all of the following criteria to be eligible to participate:

- 1) Age 65 through 74 years at the time of enrollment and are ambulatory and live in Marshfield, Wisconsin or surrounding communities.
- 2) Willing and able to give informed consent prior to study enrollment.
- 3) Able to comply with study requirements.

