### **6.4.1 Influenza Vaccination Status**

The availability and types of influenza vaccines vary from season to season. Vaccination status and vaccine types received will be obtained for prior seasons for all participants.

We have previously validated the use of the local immunization registry at Marshfield Clinic, RECIN, to correctly categorize receipt of influenza vaccine. Since RECIN exchanges records with the Wisconsin Immunization Registry, all vaccines administered by public health immunization providers will be identifiable. Immunization records have sufficient detail to

distinguish inactivated vaccine types, and to distinguish different manufacturers and lot numbers.

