### **12.2 Analyses Addressing Objectives**

#### **12.2.1 Analyses of Primary Objectives**

After log transformation of the antibody titers, geometric mean antibody titers (GMT) pre- and post- vaccination will be compared within subjects by vaccine type. For the primary aim, adults receiving high dose trivalent inactivated influenza vaccine will be compared with those receiving aIIV3.

The mean and standard deviation of log titers will be calculated. Linear mixed-effects models will be used to adjust for variables such as age, given the potential for small differences in age and the known difference in GMT by age, baseline antibody titer and prior season vaccination status. The mean fold rise (MFR), defined as the mean of the ratio of post vaccination GMT and pre-vaccination GMT for each subject, between the groups will be computed from mixed-effects model along with its associated 95% confidence interval (CI). For the declaration of non-inferiority of GMT between groups, the lower bound of the adjusted 95% CIs for the GMT ratios will be determined for each strain.

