#### **12.2.2 Analyses of Secondary Objectives**

Analyses of virus neutralizing antibody titers, neuraminidase antibody mediated inhibition titers, and anti-human CD107a antibody titers will be similar to HI data described above. Secondary analyses will also include comparisons of GMT for HI and neuraminidase inhibition assays, seroconversion rates, and ADCC measures by prior season vaccination and vaccine type in the current season.

If vaccine failures (RT-PCR confirmed influenza infection) occur, we will assess factors associated with failure using logistic regression, including vaccine type.

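### The secondary repeat-versus-switch contrasts (A v C1, B v C2) are only partly randomised for the 2016-17 vaccine, and the plan neither names the Fall-2017 recruitment stratum nor plans an analysis limited to those randomised in Year 1

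*Combined protocol and SAP*

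**What the plan says.** **Groups.** Section 3.1 randomises up to 180 people in Fall 2016 to IIV3, HD-IIV3 or aIIV3. Table 1 gives A (HD-IIV3 twice) and B (aIIV3 twice) 60 each, and C1, C2 and C3 (IIV3, then HD-IIV3, aIIV3 or RIV4) 30 each. Part of C comes from outside Year 1: "An additional 30 adults who received IIV3 in the 2016-2017 season will be recruited in Fall 2017". These recruits are randomised to the 2017-18 vaccine only. The synopsis (Study Design) also allows withdrawn subjects to be replaced at the start of the 2017-18 season.

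**Contrast.** Section 2.2 compares people given IIV3 in 2016-17 and then "HD-IIV3 or aIIV3 with subjects who received repeat influenza vaccination (2016-17 and 2017-18) with HD-IIV3 and aIIV3". A parallel objective does the same for the neutralisation, neuraminidase and CD107a titers.

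**Randomisation.** For Fall 2017, Section 3.3 says that "subjects will be stratified based on participation in this study during the 2016-17 season (previously participated or new recruit".

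**Analysis.** Section 12.2.1: "Linear mixed-effects models will be used to adjust for variables such as age, given the potential for small differences in age", going on to the "known difference in GMT by age, baseline antibody titer and prior season vaccination status". Section 12.2.2 adds comparisons of HI, neuraminidase inhibition, seroconversion and "ADCC measures by prior season vaccination and vaccine type in the current season". Neither section names the recruitment stratum, says which visit supplies the baseline titer in Year 2, or plans an analysis limited to people randomised in Year 1.

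**Data on recruits.** Section 6.4.1: "Vaccination status and vaccine types received will be obtained for prior seasons for all participants". Under Section 6.3 recruits have three visits, starting at Visit 4.

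**The concern.** A v C1 and B v C2 are the only planned group contrasts that hold the 2017-18 vaccine fixed and vary the 2016-17 vaccine. They are how the trial addresses the order of vaccine types, which Section 1 links to vaccine policy. Among Fall-2016 participants that comparison is randomised. Pooling in the recruits mixes it with a comparison between cohorts, and any cohort difference in titer would be read, in part, as an effect of the 2016-17 vaccine.

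The named covariates do not identify the cohort. Everyone in C1 to C3 had IIV3 in 2016-17, so prior-season status cannot separate recruits from previous participants, and in A v C1 it is the exposure itself. One cohort difference follows from the eligibility rule. The criterion is "Age 65 through 74 years at the time of enrollment", so at Visit 4 Fall-2016 participants are about 66 to 75 and recruits 65 to 74. Adjustment for age at enrollment would miss this; the plan does not say when age is taken.

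A linked point concerns the baseline titer. Recruits have no titer before Visit 4. In A v C1 and B v C2 the Visit 4 titer is a 12-month outcome of the 2016-17 vaccine (Section 2.1 treats it as one), so adjusting for it can remove part of the effect sought.

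**Working it through.** **1. Composition of the C arms.** Inputs are from Section 3.1 and Table 1; 1:1:1 allocation is implied by 30/30/30 but not stated.
- Year-1 IIV3: 180 − 60 − 60 = 60. Group C: 60 + 30 = 90 = 3 × 30. Total: 60 + 60 + 90 = 210, which reproduces Table 1.
- Per C arm: 60/3 = 20 previous participants and 30/3 = 10 recruits, so recruits are 33%.
- Assumed loss of 10% or 20% of Year-1 participants, no replacement: 10/28 = 36% or 10/26 = 38%.
- Same losses in C, replaced so that each arm stays at 30: 12/30 = 40% or 14/30 = 47%.

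**2. Shift in the pooled contrast.** If recruits' titers differ by a factor f, the C1 or C2 GMT moves by f^(1/3) − 1 before covariate adjustment. The documents give no f, so these values are assumed. The last column is the rejection rate of an unadjusted two-sided 5% t-test of pooled A v C1 with no true difference, at an assumed SD of 1.5 log2 (40,000 simulated trials).

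| f | GMT shift | Rejection rate |
|---|---|---|
| 1.2 | 6% | about 6% |
| 1.5 | 14% | about 9% |
| 2.0 | 26% | about 16% |

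Fall-2016 participants alone stay at about 5%, given no selective loss before Visit 4.

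**3. Precision of A v C1** (variance in units of SD²; power two-sided 5% for a 2-fold difference at SD 1.5, no titer covariate).

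| Analysis | Variance | SE v pooled | Power |
|---|---|---|---|
| Pooled 60 v 30 | 1/60 + 1/30 = 0.0500 | 1 | 84% |
| Five groups + common recruit term, all 210 | 0.0500 + (1/9)(0.0500) = 0.0556 | 1.054 | 80% |
| Fall-2016 only, 60 v 20 | 1/60 + 1/20 = 0.0667 | 1.155 | 72% |

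In the second row, the recruit effect is estimated within three arms of 20 v 10, with variance (1/20 + 1/10)/3 = 0.0500, and enters the contrast with weight 1/3. A recruit term in a two-group A v C1 model gives the third row, because A has no recruits.

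**4. When removing the recruit effect pays.** Mean squared error is lower than for the pooled analysis only if (log2 f / 3)² exceeds SD² × (added variance).
- Recruit term: log2 f = 3 × SD × √0.00556, so f = 1.17, 1.26 and 1.36 at SD 1.0, 1.5 and 2.0.
- Fall-2016 only: log2 f = 3 × SD × √0.0167, so f = 1.31, 1.50 and 1.71.

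**5. Visit 4 titer.** If Visit 4 GMTs differ by a factor g in the same direction as the effect and the regression slope is b, adjustment lowers the GMT ratio by 1 − g^(−b). For assumed b of 0.5 to 0.7: 5-6% (g = 1.1), 9-12% (g = 1.2), 18-25% (g = 1.5). If the Visit 4 difference runs the other way, adjustment enlarges the contrast.

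**6. Precision given up without the Visit 4 titer.** With an assumed correlation r of 0.6 to 0.7, and against a pooled analysis adjusted for that titer:
- Five-group model without it: SE ratio 1.054/√(1 − r²) = 1.32 to 1.48.
- Fall-2016 only without it: 1.155/√(1 − r²) = 1.44 to 1.62.
- For the same 2-fold difference at SD 1.5, the Visit 4-adjusted pooled analysis has 96-98% power, against 80% and 72% in step 3. These analyses target different effects.
- Fall-2016 only with the Visit 1 titer (assumed r of 0.4 to 0.6): 1.155 × √(1 − r²) = 1.06 to 0.92 times the pooled SE without a titer covariate.

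**The case against.** The strongest reply is that nothing shows the cohorts differ. Section 6.1 says the second enrollment follows the same recruitment procedures, and Sections 5 and 6.2 apply one age range, one clinic population and one set of criteria. Age is a named covariate, and a one-year shift in age limits is a small difference. This stands: a reader might infer that the pooled contrasts are biased, but the documents support only that they are open to a bias of unknown size. The 1.5- and 2-fold offsets are illustrations.

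Second, the covariate list is introduced with wording that leaves it open. A reader might infer that the stratum is excluded from the models; it is unspecified, and the analyst could add it.

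Third, correcting for recruits has a price. By step 4, a recruit term makes the estimate worse on mean squared error below about a 1.26-fold offset at SD 1.5, and restriction does so below about 1.50-fold. The recruit term also assumes the same offset in C1, C2 and C3. This stands, and is why the restricted result belongs beside the pooled one and the recruit term is optional.

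Fourth, Section 1 says response depends on pre-existing antibody, so a titer-adjusted contrast is a legitimate quantity. Agreed, if it is labelled as such. What remains is that the only fully randomised version of A v C1 and B v C2 is not planned.

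**Conclusion.** The concern holds in a limited form. A v C1 and B v C2 are randomised for the 2016-17 vaccine in about two thirds of each C arm. The recruit share is 33% on the planned numbers, 36-38% with 10-20% loss, and 40-47% if losses in C are replaced. The possible shift in the C1 or C2 GMT is 6%, 14% or 26% for assumed offsets of 1.2-, 1.5- and 2-fold, before covariate adjustment; the true offset is undocumented and may be near one. The Visit 4 adjustment is a separate ambiguity, worth 5-25% of the GMT ratio under the assumptions in step 5.

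A reader might extend this to the primary comparison or to the whole of Year 2. The documents do not support that. A and B contain no planned recruits, so A v B is unaffected unless replacements are enrolled there. C1 v C2 v C3 is randomised within the recruitment strata. The point concerns secondary objectives for which Section 12.3 claims no power, and it calls for a clarification of the SAP.

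**What to change.** 1. **C1 v C2 v C3:** include the recruitment stratum, with the Visit 4 titer as baseline. Cost: one degree of freedom.
2. **A v C1 and B v C2:** report the analysis in Fall-2016 randomised participants (about 60 v 20, subject to retention to Visit 4) beside the pooled result, and describe any pooled result as partly non-randomised. Cost: SE up 15.5% against pooled 60 v 30. The Visit 1 titer is an optional covariate here. Section 8.1 plans Visit 1 sera against 2016-17 strains, so use the 2016-17 strain of the same subtype or lineage. A five-group model with a common recruit term (SE up 5.4%) is an optional alternative; state its common-offset assumption.
3. **Covariates and flags:** use age at Visit 4, and identify any replacement enrolled in A or B as a Fall-2017 recruit.
4. **Visit 4 titer in A v C1 and B v C2:** state that it is a 12-month outcome of the 2016-17 vaccine. Results adjusted for it, and MFR and SRR, which build it in, describe the response given the pre-vaccination titer and not the total effect of the 2016-17 vaccine.

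No new visits, subjects or assays are needed, and the stratum is already used in the randomisation. The main downside is that total-effect analyses are less precise: against a pooled analysis adjusted for the Visit 4 titer, the SE is 32-48% wider for the five-group model and 44-62% wider for the restricted analysis with no titer covariate (assumed correlation 0.6 to 0.7).

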## 3.2 Study Endpoints

### 3.2.1 Primary Endpoints

- Hemagglutinin inhibition antibody levels specific for vaccine strains and representative strains of circulating influenza viruses. Endpoints based on these data will include geometric mean titers (GMT), mean fold rise (MFR), seroresponse rate (SRR), and seroprotection rate (SPR).
  - Seroresponse rate defined as the proportion of subjects with paired samples with prevaccination HI titer <1:10 and postvaccination (day 28) HI titer ≥1:40 or at least a 4-fold increase in HI from prevaccination HI titer ≥1:10.
  - Seroprotection rate defined as the proportion of subjects with postvaccination HI titer ≥1:40.

### 3.2.2 Secondary Endpoints

- Virus neutralizing antibody titers, neuraminidase antibody mediated inhibition titers, and anti-human CD107a antibody titers specific for vaccine strains and representative strains of circulating influenza viruses. Endpoints based on these data will include geometric mean titers (GMT) and mean fold rise (MFR).
- RT-PCR confirmed influenza

## 3.3 Randomization Procedure

We will use stratified block randomization to ensure more even distribution of subjects with prior receipt of 2015-16 influenza vaccine. Subjects will be stratified based on receipt of 2015-

16 influenza vaccine. Within each group (vaccinated or unvaccinated in 2015-16), sequential enrollment numbers will be randomly assigned to each vaccine group in random blocks ranging from four to eight. This will ensure proper distribution of subjects across vaccine group assignment.

In Fall 2017, only participants who received IIV in 2016-17 will be randomized. We will use stratified block randomization and subjects will be stratified based on participation in this study during the 2016-17 season (previously participated or new recruit).

This is an open-label study, therefore the vaccine type will be known to the participant. Trained research staff will prepare and administer the influenza vaccine. Randomization to vaccination type will occur at the participant's first study visit after eligibility is confirmed and informed consent obtained. Those enrolled in year 1 who receive IIV3 will be randomized a second time at their fourth visit.

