## **6 STUDY PROCEDURES**

### **6.1 Enrollment Period**

Enrollment in this study will begin when influenza vaccine is available through the Marshfield Clinic, typically in August or September 2016, and will continue until the target sample size for each group is reached or all eligible adults have been contacted with the goal of completing all baseline study visits by the end of October 2016. The second enrollment period for the additional 30 subjects will follow the same recruitment procedures in Fall 2017.

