#### **6.3.1.2 Influenza vaccine**

Individuals will receive either 1) IIV3, 2) HD-IIV3, or 3) aIIV3 according to a pre-assigned randomization scheme. Trained research staff will administer all vaccines.

Individuals with fevers will be rescheduled regardless of the vaccine to be received. Vaccinations will be recorded in the electronic immunization registry, and vaccine information sheets will be provided.

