#### **6.3.4.2 Enrollment and Vaccination of New Recruits**

Research staff will meet with eligible individuals to review study requirements and obtain written consent. A brief questionnaire may be administered to obtain additional information regarding demographics and relevant exposure and medical history. We will also request permission from individuals to access their electronic medical record in order to obtain data related to medical history, medication use, and vaccination history. The remaining study visits will be scheduled.

All participants will have a baseline blood draw for measurement of antibody titers (20 mL [4 teaspoons]), hemagglutination inhibition [HI] and other assays (see below). Serum from the samples will be prepared, frozen, and tested per current protocol (see laboratory methods). Additional measures of humoral immune function may also be examined. Participants will receive either 1) HD-IIV3, 2) aIIV3, or 3)RIV4 according to a pre-assigned randomization scheme. Trained research staff will administer all vaccines.

Individuals with fevers will be rescheduled regardless of the vaccine to be received. Vaccinations will be recorded in the electronic immunization registry, and vaccine information sheets will be provided.

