### **12.3 Power Considerations**

Study sample size was based on available resources. For the analysis on HI titers, a sample size of 60 per group will provide over 90% power using a one-sided, two-sample t-test to conclude that one vaccine group is superior as defined by rejecting a null hypothesis of equality if the GMT values differ by approximately 20%.

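### Do Year 1 blocks of four to eight, shared among three vaccine groups, put the planned 60 per group at risk?

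*Combined protocol and SAP*

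**What the plan says.** Section 3.3 (Randomization Procedure) stratifies Year 1 by receipt of 2015-16 vaccine. Within each stratum, "sequential enrollment numbers will be randomly assigned to each vaccine group in random blocks ranging from four to eight". It adds: "This will ensure proper distribution of subjects across vaccine group assignment". No allocation ratio is stated, and nothing is said about a block that does not divide by the number of groups.

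Section 6.3.1.2 names the three Year 1 vaccines and points to a separate list: "Individuals will receive either 1) IIV3, 2) HD-IIV3, or 3) aIIV3 according to a pre-assigned randomization scheme". Section 6.3.4.2 does the same for the Fall 2017 recruits: "Participants will receive either 1) HD-IIV3, 2) aIIV3, or 3)RIV4 according to a pre-assigned randomization scheme". Neither list is reproduced. Section 3.3 calls for stratified blocks in Fall 2017 without giving a size.

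On numbers, Section 3.1 sets a Year 1 ceiling of 180, and Table 1 shows 60 in each of groups A and B and 30 in each of C1 to C3. Section 6.1 says enrollment "will continue until the target sample size for each group is reached or all eligible adults have been contacted", and then: "The second enrollment period for the additional 30 subjects will follow the same recruitment procedures in Fall 2017". Section 12.3 states that "a sample size of 60 per group will provide over 90% power using a one-sided, two-sample t-test".

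**The concern.** Permuted blocks normally have sizes that are multiples of the number of arms, because that is what makes each completed block balanced. Here four of the five possible sizes are not multiples of three, yet Section 3.3 presents the blocks as securing proper distribution. Whether they do depends on how the leftover places are filled, which is not stated.

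Three consequences could follow.

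- If leftover places always went to the same groups in a set order, the groups would be unequal by design, and the primary comparison of HD-IIV3 with aIIV3 would no longer be 60 v 60.
- The ceiling of 180 equals 3 × 60, so any excess in one group is a shortfall in another. If Section 6.1 requires every vaccine group to reach its target, the ceiling and the target cannot usually both be met.
- If a group were closed once it reached 60, the last assignments would be shared between two vaccines. In an open-label study staff could notice this and guess the next assignment more easily.

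At stake would be some power in the primary comparison and some concealment near the end of enrollment.

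**Working it through.** **Inputs.** Three groups, blocks of four to eight and two strata (Sections 3.1 and 3.3); a ceiling of 180, with about 25% unvaccinated in 2015-16 (Section 3.1), so strata of about 0.25 × 180 = 45 and 135; 60 per group (Table 1, Section 12.3). Assumed, because the documents do not say: sizes 4, 5, 6, 7 and 8 are equally likely.

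**The plan's own totals.** C1 to C3 sum to 90; less the 30 recruited in Fall 2017, this leaves 60 on IIV3 in Year 1. Then 60 + 60 + 60 = 180, and 180 + 30 = 210. Both stated totals are reproduced, and the slack is 180 − 3 × 60 = 0.

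**Divisibility.**

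| Block size | Full sets of three | Places left over |
|---|---|---|
| 4 | 1 | 1 |
| 5 | 1 | 2 |
| 6 | 2 | 0 |
| 7 | 2 | 1 |
| 8 | 2 | 2 |

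**Leftover places given to different groups at random.** By symmetry each group expects 180 / 3 = 60. In 20,000 simulated lists, HD-IIV3 and aIIV3 differed by 3.3 on average (95th percentile 8). The smallest of the three groups averaged 57.5 (5th percentile 55). Exactly 60/60/60 occurred in 3% of lists.

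**Comparison with sizes that do divide by three.** Sizes 3, 6 and 9 gave exactly 60/60/60 in 47% of lists and a smallest group of 59.4 on average. Blocks of 6 alone gave exact equality in about 22%, because 135 / 6 = 22.5 and 45 / 6 = 7.5 both end in half a block. Even conventional blocks would therefore often miss exact equality. The practical gain is 59.4 − 57.5 = 1.9 subjects in the smallest group.

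**Power.** Section 12.3 gives neither a standard deviation nor a significance level, so its figure of over 90% cannot be rebuilt. Instead, the standardized difference d is set to give exactly 90% at 60 v 60 in a one-sided two-sample t-test: d = 0.537 at level 0.05 and 0.597 at 0.025. Power then follows from the noncentral t distribution with noncentrality d / √(1/n₁ + 1/n₂).

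- 55 v 65: the equivalent equal group size is 2 × 55 × 65 / 120 = 59.6, and power is 89.8% at either level.
- This split differs by 10, more than the 95th percentile of 8, so the loss of 0.2 percentage points is already a pessimistic figure.

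**Fixed-order fill, for contrast.** Full sets per block average (1 + 1 + 2 + 2 + 2) / 5 = 1.6 per group. The first group in the order gains a place in four of the five sizes (0.8), the second in two (0.4), the third in none. Per block of mean size 6 this gives 2.4, 2.0 and 1.6; over 180 / 6 = 30 blocks it gives 72, 60 and 48. Power at one-sided 0.05 depends on where the two primary groups fall in the order:

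| Primary pair | Power |
|---|---|
| 72 v 60 | 92.1% |
| 72 v 48 | 88.9% |
| 60 v 48 | 86.7% |

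The vaccine order in Section 6.3.1.2 would give 60 v 48. The order in Table 1 would give 72 v 60, which is better than 60 v 60.

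**Ceiling against target.** Section 3.3 uses the word group for the two prior-vaccination strata as well as for the vaccine arms. Section 6.2 ties batches of mailed invitations to the sample size in each group. Invitations can be steered by vaccination history. They cannot be steered by vaccine arm, which is assigned only after consent. Section 6.1 can therefore be read as referring to strata, and on that reading it does not conflict with the ceiling.

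**The case for a change.** The strongest case for acting is that the text really is incomplete and completing it costs little. A reader cannot tell from Section 3.3 that allocation is 1:1:1, or what happens in a block of 4, 5, 7 or 8. If Section 6.1 means vaccine arms, no section says whether the ceiling or the target prevails. Recruiting until every arm had 60 would, on the same assumptions, take about 187 subjects on average, 7 over the ceiling. Fall 2017 enrollment was still ahead when Version 3.0 was issued, and its C groups are small.

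The incompleteness stands; the consequences drawn from it do not. Section 3.3 ties random assignment to sequential enrollment numbers, and Section 6.3.1.2 to a list prepared in advance. The ordinary course is to take the next entry on the list until enrollment stops. Nothing suggests a fixed-order fill or the closing of a group. The overrun arises only on one of two readings of an ambiguous word, while 180 is worded as an upper limit and Section 12.3 says that the sample size was set by available resources. No defect is shown for Fall 2017: leaving the block size out of the protocol helps concealment, and Section 6.1 carries over the recruitment procedures, not the block sizes.

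**Conclusion.** The concern is right on the arithmetic: only a block of 6 divides by three, the 1:1:1 ratio is implied and not written, and leftover places are not mentioned. No change to the plan follows. Followed as written, with random assignment inside random blocks, allocation is unbiased, the two primary groups differ by about 3 subjects on average, and a 55 v 65 split costs 0.2 points of power. Blocks in multiples of three would add about 2 subjects to the smallest group and would alter no result or conclusion.

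The sizes rest on block sizes 4 to 8 being equally likely, strata of 135 and 45, leftover places filled at random, and power of exactly 90% at 60 v 60. A fixed-order fill would change the group sizes more, but the documents give no sign of one, and its effect on power could go either way. The block sizes and the handling of leftover places belong in the randomization list, and an ordinary account of the allocation when results are reported covers them.
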